8.8.3 Vital signs

Absolute value and changes from baseline for vital sign measurements (heart rate, systolic and diastolic blood pressure) will be summarized by treatment group and position (at each scheduled visit using descriptive statistics. For systolic and diastolic blood pressure the values collected when sitting/lying will be summarized separately to those collected whilst standing.

Vital signs data will be listed.

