2.3 RISK/BENEFIT ASSESSMENT

2.3.1 KNOWN POTENTIAL RISKS

Potential risks are related to the long-term administration of an investigational drug to participants suffering from multiple chronic diseases.

BIO101 was well tolerated in healthy elderly volunteers receiving up to 450 mg b.i.d. for 14 days. Based on non-clinical safety (26-week studies **example 1**, safety pharmacology and phase 1 results, both immediate and long-ranging risks can be considered as low.

The active ingredient in BIO101, 20E, may become a restricted substance, which is not allowed to be used in sport competitions. The reason is that there is a tendency to use it as an anabolic agent. Since BIO101 contains a high concentration of 20E at a dose that is much higher than the one that appears in nutritional supplements, there is concern that non-sarcopenic individuals may want to use BIO101 illicitly. Participants in this study will be warned and instructed to not allow anyone to gain access to their medication and to use only according to the medication instructions provided in the drug kits.

In addition,

putative mechanism of action through activation of the MAS receptor and potential impact on the renin–angiotensin–aldosterone system (RAS) requires attention. A special surveillance and precaution will be taken with events that could theoretically indicate presence of orthostatic hypotension (OTH), including dizziness and presyncope related to orthostatic changes and actual measurements. In addition, events that comply with the clinical definition of OTH (i.e. decrease in systolic blood pressure of 20 mm Hg or a decrease in diastolic blood pressure of 10 mm Hg within three minutes of standing when compared with blood pressure from the sitting or supine position) will require special attention even without symptoms.

There are limited risks linked to the execution of the functional tests, e.g. falling during a test. The investigational site staff will put in place adapted surveillance, adequate prevention including cancellation or postponing of a planned test, and adapted emergency care in order to prevent, limit and appropriately and timely treat possible adverse events.

All AEs will be reported as per standard pharmacovigilance procedures (Section 8.4).

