8.2 SAFETY AND OTHER ASSESSMENTS

Several procedures and evaluations in SARA-INT clinical protocol will be performed to monitor the study intervention's safety. Some of those are necessary for other purposes (e.g., screening, eligibility, and enrollment).

• **Physical examination:** a standard medical exam of all organ systems to detect possible concomitant conditions that could represent an exclusion criterion (e.g. food ulcer, lower limbs arterial insufficiency, severe respiratory condition, etc.)

- **Anthropometry**: includes height and weight, subcutaneous tissue thickness (with the help of a plicometer) and various circumference measurements
- Short Form -Mini Nutritional Assessment (SF-MNA): this is a 6-question short form of the MNA that can be completed in 5 minutes or less. The MNA has been validated in international studies with a broad range of HCPs in a variety of settings. Currently, this instrument is administered by healthcare professionals to determine patients' nutritional status (Huhmann et al, 2013)⁶¹
- Vital signs (pulse and blood pressure) are measured at screening, M1, M3 and M6 (or endof-study) visits. These are measured twice, in lying or sitting and standing positions
- Electrocardiograms (ECGs): this is performed for screening purposes only. It will be read locally, in order to exclude any underlying cardiac diseases that could represent an exclusion criteria. Meaningful abnormalities will be reported on the eCRF. The original will be kept in the source documents. This should be conducted prior to the start of any physical functional assessments (e.g. the 400MW test) for the safety of the study participants
- Radiographic or other imaging assessments: 1) DEXA scan in SARA-INT is mostly devoted to assess body composition in terms of appendicular lean body mass, at screening visit and M6 (or end-of-study visit). DEXA scans could be performed up to 8 weeks before randomization and enrollment. 2) Gallbladder ultrasound: this is required during screening to exclude previous or active hepatobiliary diseases (e.g. cholestasis/biliary tract obstruction, cholelithiasis, cholecystitis, etc.), and is repeated at the end of the treatment (M6 visit) to assess any emergent hepatobiliary abnormalities

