8.3.8 EVENTS OF SPECIAL INTEREST

In this study, falls and injurious falls as well as orthostatic hypotension are considered events of special interest.

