9.4.5 SAFETY ANALYSES

Safety variables will be summarized/analyzed by groups of treatment, on the Safety population.

Vital signs, biochemistry and hematology parameters will be described by descriptive statistics, for the entire period of the study and at each timepoint.

Usual tables (by SOC and preferred term) will be produced for AEs (falls, injurious falls and orthostatic hypotension will be tabulated separately) after coding with the MEDRA terms.

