8.8.1 Adverse events

All AEs or treatment emergent adverse events (TEAEs) will be classified by Primary SOC and PT according to MedDRA Version 21.0 or higher.

AEs will be classified as pre-treatment AEs, TEAEs (treatment-emergent adverse events), or post-treatment AEs, defined as follows:

Pre-treatment AE: any AE that started before the first dose date of study drug intake (AE onset date < date of first study drug intake).

Treatment-emergent: An AE will be considered a TEAE if it starts on or after the first dose date of study drug up to the last dose date + 6 weeks (date of first randomized study medication intake \leq AE onset date \leq last dose date + 6 weeks).

Post-treatment AE: any AE that was newly developed after the last dose date + 6 weeks (AE onset date > last dose date + 6 weeks).

Details for imputing missing or partial start dates of adverse events are described in Section 7.1.4.

Summaries of the following will be presented.

An overall summary table with number and percentage of subjects and number of events for the following will be presented by treatment group and overall:

- All AEs (excluding pre and post treatment events)
- All TEAEs
- Treatment related TEAEs (AE will be defined as related if causality is either definitely, probably or potentially)
- Treatment related Serious TEAEs (AE will be defined as related if causality is either definitely, probably or potentially)
- TEAEs by maximum severity (if a subject has several AEs with the same SOC/PT. The AE will be included only once in the summary, this being the AE with maximum severity
- TEAEs leading to treatment discontinuation (action taken = 'Discontinued')
- Serious AEs/TEAEs
- TEAEs leading to death.
- Adverse events of special interest (AESI) (falls and injurious falls and orthostatic hypotension)
- Serious Adverse events of special interest (AESI) (falls and injurious falls and orthostatic hypotension

Version Final 2.0, Date: 04JUN2021

• Treatment related Adverse events of special interest (AESI) (falls and injurious falls and orthostatic hypotension)

Pre-treatment AEs and post-study AEs will be presented in the listings only.

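### The SAP never derives the paired fall in blood pressure that defines orthostatic hypotension in the protocol, so a measured drop is counted by arm only if an investigator reports it as an adverse event

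*SAP*

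**What the plan says.** Protocol 2.3.1 asks for special surveillance of orthostatic hypotension because of the drug's putative action on the renin-angiotensin system. Its criterion is a "decrease in systolic blood pressure of 20 mm Hg or a decrease in diastolic blood pressure of 10 mm Hg within three minutes of standing", relative to the same person's sitting or supine pressure, and events that meet it "will require special attention even without symptoms". Protocol 8.3.8 makes the condition an event of special interest: "falls and injurious falls as well as orthostatic hypotension are considered events of special interest".

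The readings needed for the criterion are collected. Protocol 8.2 says of the vital signs: "These are measured twice, in lying or sitting and standing positions".

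On analysis, Protocol 9.4.5 promises descriptive statistics for vital signs and, for adverse events, that "falls, injurious falls and orthostatic hypotension will be tabulated separately". SAP 8.8.1 carries the second part out by listing "Adverse events of special interest (AESI) (falls and injurious falls and orthostatic hypotension" among the categories presented by treatment group, with serious and treatment-related versions. For the pressures themselves, SAP 8.8.3 summarises absolute values and changes from baseline by arm, visit and position: "For systolic and diastolic blood pressure the values collected when sitting/lying will be summarized separately to those collected whilst standing". The only other vital-signs output is a listing: "Vital signs data will be listed". The derived variables in SAP Table 1 include neither a postural difference nor an orthostatic flag.

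**The concern.** The definition is paired: it compares two readings from one person at one visit. Separate summaries by position discard that pairing, so the number of participants who meet the definition cannot be read from the planned tables, by arm or overall.

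The adverse event route fills the gap only in part, because it depends on reporting. Protocol 7.1 has new findings reported as adverse events when they are judged clinically relevant. No text requires every reading that crosses the thresholds to be reported, and SAP 8.8.1 does not say how events of special interest are identified. Asymptomatic drops, which the protocol expressly brings into scope, are the ones most exposed to variable reporting between sites.

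At stake is a safety signal that the sponsor itself declared, in older adults at risk of mobility disability for whom falls are also an event of special interest. If qualifying drops were more frequent on active drug but seldom reported, the data to show it would be in the database and the listings, but in no table.

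**Working it through.** **What is planned for each part of the definition**

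| Element | Collected? | Derived in the SAP? | Counted by arm? |
|---|---|---|---|
| Sitting/lying pressure | Yes (Protocol 8.2) | Summarised alone (SAP 8.8.3) | As descriptive statistics |
| Standing pressure | Yes (Protocol 8.2) | Summarised alone (SAP 8.8.3) | As descriptive statistics |
| Within-person difference | Implied by the pair | No (not in Table 1 or 8.8.3) | No |
| 20/10 mmHg threshold | Implied by the pair | No | No |
| Orthostatic hypotension reported as an adverse event | Yes | Yes (SAP 8.8.1) | Yes |

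The documents give no expected rate, postural SD or correlation, so there is no figure of the plan's own to reproduce. What follows illustrates the gap with **assumed values**. It covers systolic pressure only and reads the criterion as a fall of at least 20 mmHg.

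**Can the separate summaries yield the count?**

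Let each position have standard deviation SD, let m be the mean fall on standing, and let r be the within-person correlation between positions. Under bivariate normality:

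- SD of the fall = SD × √(2(1 − r))
- share falling by at least 20 mmHg = 1 − Φ((20 − m) / SD of the fall)

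Take SD = 15 mmHg and m = 5 mmHg. Counts use the 77 per arm in SAP Figure 1.

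| r | SD of the fall | (20 − 5) / SD of the fall | Share | Of 77 |
|---|---|---|---|---|
| 0.5 | 15 × √1.0 = 15.00 | 1.00 | 15.9% | 12.2 |
| 0.8 | 15 × √0.4 = 9.49 | 1.58 | 5.7% | 4.4 |
| 0.9 | 15 × √0.2 = 6.71 | 2.24 | 1.3% | 1.0 |

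The mean and SD in each position are the same in all three rows; only r differs, and the SAP does not report it. Over SD 15 to 18, m 2 to 5 and r 0.5 to 0.95, the share runs from about 0.01% (SD 15, m 2, r 0.95) to 20.2% (SD 18, m 5, r 0.5).

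**What a modest shift in the mean does to the share**

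Suppose the mean fall is 5 mmHg on placebo and 8 mmHg on active drug, with the same SD of the fall in both arms.

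| SD of the fall | Share at mean fall 5 | Share at mean fall 8 |
|---|---|---|
| 10 | 6.7% | 11.5% |
| 12 | 10.6% | 15.9% |
| 15 | 15.9% | 21.2% |

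For SD 12, (20 − 5)/12 = 1.25 and (20 − 8)/12 = 1.00. With complete pairs, a reader could recover the 3 mmHg difference by subtracting the two position means in each arm. The change in the share could not be recovered.

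**Limits on the readings**

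- Protocol 8.2 places vital signs at screening, M1, M3 and M6 or end of study. The COVID schedule in Protocol 1.3 replaces M1, M3 and M6 with telephone calls and marks vital signs only at Day 0 and at week 39 or end of intervention. Affected participants may have one post-baseline pair.
- The definition requires the fall within three minutes of standing. Protocol 8.2 gives no time for the standing reading.

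**The case against.** A reader might infer more than the documents support.

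- **That nobody is classified and asymptomatic cases are never counted by arm.** This is not so. An investigator may report a measured drop, symptomatic or not, as orthostatic hypotension, and SAP 8.8.1 then counts it by arm. Protocol 8.2 has participants asked at each visit about new symptoms and newly observed abnormalities. The protocol's summary of changes says the term was added after a new adverse event was reported in the study, so the route is in use.
- **That dizziness and presyncope disappear.** They are outside the stated special-interest grouping, but if reported as treatment-emergent events they appear in the general tables by system organ class and preferred term. Regrouping them is a matter of presentation.
- **That only means are shown.** SAP 8.1 also specifies the SD, confidence interval, median, minimum and maximum. SAP 8.8.3 adds a listing that contains the individual readings.
- **That the SAP breaks a promise in the protocol.** Protocol 9.4.5 commits to descriptive vital-sign statistics and a separate tabulation of the reported events. The SAP provides both, and no text requires classification from the readings.

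It can also be said that Protocol 2.3.1 is an instruction for surveillance rather than an analysis definition, and that a derived flag could not fully reproduce a criterion with a time limit.

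These points narrow the finding but do not remove it. A minimum or maximum taken within one position says nothing about the paired fall, a listing is not a count, and the adverse event tables depend on what was reported. The timing point stands and has to be stated with the table.

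**Conclusion.** The point holds in this form: the SAP does not apply the protocol's definition of orthostatic hypotension to the pressures that the trial measures. Qualifying drops are counted by arm only when reported as adverse events, and the rest can be found only in listings.

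The size is unknown. The percentages above are illustrations that rest on assumed means, SDs and correlations, on normality and on systolic pressure alone. What does not depend on those values is that separate position summaries do not determine the number meeting a paired criterion. The documents do not show that cases are being missed or that the arms differ.

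This is a low-cost improvement to the reporting of a declared safety signal. It is neither a contradiction between the protocol and the SAP nor a threat to the efficacy analysis.

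**What to change.** In SAP 8.8.3, with a matching entry in Table 1:

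1. Derive standing minus sitting/lying systolic and diastolic pressure for each participant and visit with both readings.
2. Flag a fall of at least 20 mmHg systolic or at least 10 mmHg diastolic, the thresholds in Protocol 2.3.1.
3. Tabulate number and percent flagged by arm, at each visit with paired readings and at any post-baseline visit, split by whether the flag was present at baseline. Use the number of participants assessed as the denominator.
4. Cross-tabulate the flag against orthostatic hypotension reported as an event of special interest.
5. Add a footnote that the flag is a proxy where the time since standing was not recorded, and that participants affected by the COVID schedule may have only one post-baseline pair.

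The cost is one derived variable, one descriptive table and a short change of SAP wording, all from data already collected. The table will be thinner after the COVID schedule change because fewer paired readings exist. It needs no hypothesis test, in keeping with SAP 8.8, and no change to how participants are managed.

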8.8.4 Physical examinations

Physical examination findings (Normal, Abnormal) will be summarized using frequencies and percentages by Body System, treatment group and scheduled visit.

Physical examination data will be listed.

8.8.5 Anthropometry

Anthropometry measurements (height, weight, BMI, calf/waist/Hip/mid-arm circumference and tricipital plica thickness) will be summarized by treatment group at each scheduled visit using descriptive statistics.

Anthropometry data will be listed.

8.8.6 Electrocardiograms (ECG)

ECG data collected at screening visit will be listed.

8.8.7 Short Form Mini-Nutritional Assessment

A summary of SF-MNA score as mentioned in the Appendix at baseline using descriptive statistics and the nutritional status using frequency and percentage will be presented.

SF-MNA data will be listed.

8.9 Other analysis

8.9.1 Subgroup analysis

The subgroup analyses will use the FAS.

Subgroup analyses will be performed for the primary endpoint (change from baseline in 400MW gait speed at M6/M9) and the key secondary endpoints (change from baseline in PF-10 sub-score of the SF-36 and change from baseline to M6/M9 in Handgrip strength test).

Version Final 2.0, Date: 04JUN2021

Page 44 of 69

These pre-identified, at-high risk of worsening, subpopulations have been identified:

- Low gait speed (4 meter walk with a gait speed <= 0.8 m/s) at Screening
- Sarcopenic obesity (having a percentage of body fat mass of >25% in men and >35% in women) as measured by the DEXA at Screening
- Study subjects with a chair stand sub-score of ≤2 of the SPPB at Screening
- Study subjects who experience a deterioration. Deterioration is defined as a decrease of > 2% in the ALM or BMI value at M6/M9 compared to the Screening value.

The subgroup analyses based on these factors will be performed in order to better characterize treatment benefits in subjects with increased risk of mobility disability. The analysis will be performed in both the subpopulations identified above and the group of FAS patients that are not in the subgroup. Summaries of each subgroup by treatment will be presented and MMRM analysis per section 8.7.1.1 will be performed for the primary endpoint and PF-10. An ANCOVA method detailed in section 8.7.1.12 will be used for the analysis of change from baseline to M6/M9 in Handgrip strength test. Parameters of gait speed (400MW with a gait speed <= 0.8 m/s/400MW with a gait speed > 0.8 m/s) and sarcopenic obesity (percentage of body fat mass of >25% in men and >35% in women/ percentage of body fat mass of \leq 25% in men and \leq 35% in women) will be included in the models. Important demographics or baseline characteristics such as age, country, etc. may be defined prior to the database lock and unblinding and will be included in the model.

Least square mean difference (175mg BIO101 Vs Placebo and 350mg BIO101 Vs Placebo) and 95% CIs for each of the subgroups will be presented in forest-plots.

No adjustment for multiplicity will be performed.

A by-subject listing will be provided.

